BabyCenter LLC is a member of the Johnson & Johnson family of companies and provides global digital parenting content. The company estimates that 7 in 10 expectant moms in the United States use BabyCenter.com. Company products include websites, mobile apps, online communities, email series, social programs, and public health initiatives. We propose to use one of the online communities in this study: "Miscarriage, Stillbirth, & Infant Loss Support." <https://community.babycenter.com/groups/a15155>.

Proposed Study and Aims

We now are proposing a new pilot study (MOMSonLINE2) to evaluate recruitment specifically for women of color who are closer to the time of perinatal loss. This is a feasibility study. We will track data about group usage through a new collaboration with BabyCenter.com. Once this pilot is completed, we will have adequate data and knowledge to develop a much larger randomized control study of on-line support outcomes after perinatal loss.

Aim #1: Demonstrate the ability to recruit and retain recently-bereaved women of color to the pilot through a partnership with the Michigan Department of Health and Human Services.

Aim #2: Test a collaboration with BabyCenter which would provide proprietary data about the support group usage of our study participants and allow much more accurate tracking of use.

[figure not shown]
Aim #3: To test whether incentives based on group usage (compared with incentives based on survey completion) lead to increased engagement with the online group.

Aim #4: To test preliminary mental health outcomes (symptoms of depression, anxiety, post-traumatic stress, and grief) with a pilot group using standardized measures.

Research Methods

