Subjects will sign up for a BabyCenter account (unless they already have one), will agree to follow all the rules of the BabyCenter site and the community group, and agree to share their username with both the study team and with BabyCenter (so that BabyCenter can send us information about usage). As BabyCenter is a commercial web site, they have their own privacy rules and disclosure about what information they collect and/or share for users, described here: <https://www.babycenter.com/help-privacy>. BabyCenter automatically sends out a “daily digest” email with links to any new posts in the group which encourages members of a community support group to visit the group, and subjects in our study will get this same digest.

Participation: During the study, subjects will be asked to

- a. Sign on to the BabyCenter community group for people with pregnancy or infant loss at least 3x weekly for 6 weeks. Participants may choose to post or comment on the site but are not required to do so.
- b. Complete two on-line surveys (at the beginning and end of the study) which ask about demographics, use of social media, other types of support after the loss of their infant, satisfaction and experience with the on-line group. Both surveys will include 4 standardized instruments to measure depression (PHQ-8), anxiety (GAD-7), post-traumatic stress (PTSD-Checklist, civilian version), and grief (Perinatal Grief Scale).
- c. Receive 3 weekly text-messages from the study team (to remind them to go online to the group). BabyCenter staff can track usage patterns of participants who visit the group and are logged in. If a subject has not signed on for 4 days, information will be provided to alert the study team. We will then reach out to her by personalized text message or phone call to encourage participation and assess for barriers.
- d. Get two phone calls from the study team. The first will be made after they consent to ensure they understand the study and/or answer any questions. The second will be made in the middle of the study to assess for any problems signing on.
- e. Participate in a 10-20 minute semi-structured phone interview at the end of the 6-week study.

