Tracking Usage: BabyCenter.com has agreed to share data about use of the pregnancy/infant support group among our study subjects. We will ask subjects to stay logged in when using the BabyCenter application, or bookmark the site in their browser, and mark the box “keep me logged in.” By marking this box, they will only be logged out if they purposefully log out, change browser, or clear their cookies. BabyCenter will provide the following information for each of our participants: the day and number of visits, page views, URLs visited in the group, and data on posts, comments, and “hugs” (similar to a “like” on Facebook). At the end of the study, BabyCenter will give us aggregate, de-identified data about activity of the full group, e.g. total number of weekly users, number of weekly posts, comments, and hugs.

[figure not shown]
Risks and benefits: The study is no more than minimal risk. We are asking bereaved mothers to go to an anonymous, public online support site. They are not required to post. Several experienced group members serve as volunteer group moderators. Extensive research by our team has shown that women typically find forums for loss to be supportive and help reduce the isolation which is very common in the months after a loss. There are no direct benefits to participants, but we are hopeful that by participating, some mothers may receive support and find satisfaction from supporting others.

Incentives

One study aim is to test how incentivizing different activities impacts participation. We will randomize participants either to a group which

- a) incentivizes support group participation (\$5 per week that they go to the BabyCenter.com group at least three times and \$20 for completion of the phone interview); or
- b) incentivizes survey completion (\$10 per survey and \$30 for completion of the phone interview).

Participants in either group can earn up to \$50—they are simply compensated for different parts of the study. Subjects may withdraw at any time and will be paid for all elements they have completed at the time of withdrawal. The incentives will help to cover if participants are charged by their internet provider for text messaging.

Online Safety:

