BabyCenter has a site-wide process which allows any user to report on a post or comment they are concerned about, documented here: <https://www.babycenter.com/community-help-howto>. At the top of the loss group, there is a post which includes lists of other related support groups for loss as well as support sites outside of BabyCenter.com. Every posting and comment has the option to click a link to “Report this comment” where users can send a report to staff, to the group owners, or both. Users can also email the URL and text to [contact]. BabyCenter maintains a list of resources which include links to two national suicide hotlines: <https://www.babycenter.com/community-help-resources#articlesection16>. BabyCenter also has a section of resources at <https://www.babycenter.com/community-help-resources#articlesection1> which includes this statement:

Emergency

If you believe another person is a threat to himself, herself, or someone else, please call 911, your local police department, or any other appropriate government agency. Law enforcement officials can get help and get involved where BabyCenter cannot. However, we will cooperate with officials who contact us about any situation. They can reach us by emailing [contact].

In our surveys, we are using the PHQ-8 so will not be asking about suicidal thoughts. Nevertheless, we will include information about a toll-free 24-hour suicide hotline as a resource; the number will be placed in the survey, after the PHQ-8.

Analysis:

This single-arm feasibility study will primarily be descriptive and provide summary-type information. While we will assess mental health and grief outcomes, we recognize it is not powered for significance. It is meant to demonstrate ability to recruit, retain, and engage users and will also give preliminary data on our primary outcomes, including willingness of participants

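### Does outreach triggered by 4 days without sign-on undermine the incentive comparison in Aim 3?

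*Combined protocol and SAP*

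**What the plan says.** Aim #3 (Proposed Study and Aims) is "To test whether incentives based on group usage (compared with incentives based on survey completion) lead to increased engagement with the online group". The Incentives section repeats the purpose ("One study aim is to test how incentivizing different activities impacts participation") and randomises women to payment for using the group or payment for completing surveys.

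Under Participation, every woman is asked to sign on "at least 3x weekly for 6 weeks". Item c gives all women the same scheduled reminders ("Receive 3 weekly text-messages from the study team (to remind them to go online to the group") and then adds a conditional contact: "If a subject has not signed on for 4 days, information will be provided to alert the study team". It continues: "We will then reach out to her by personalized text message or phone call to encourage participation and assess for barriers".

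Tracking Usage lists the data supplied by the site: "BabyCenter will provide the following information for each of our participants: the day and number of visits, page views", and further activity measures. Contacts made by the study team are not on that list. The Analysis section opens with "This single-arm feasibility study will primarily be descriptive and provide summary-type information" and does not mention lapse contacts.

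**The concern.** The scheduled texts and the two planned calls are the same for all women. Lapse outreach is the only staff contact whose amount depends on behaviour after randomisation, and that behaviour is the outcome of Aim 3. If payment for use works, women paid for surveys will lapse more often and be contacted more often, and each contact urges them back to the group. The observed difference then reflects payment together with unequal staff effort, and it may understate what payment alone would do.

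The pilot is meant to inform a much larger randomised trial. Without a record of contacts, its planners could not say how much staff effort accompanied each incentive, and the plan states no such record.

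**Working it through.** **Inputs from the plan.** Follow-up is 6 × 7 = 42 days. The trigger is 4 days without sign-on. The target is three sign-ons a week. Expected enrolment is 200 × 0.20 = 40, which reproduces the stated figure. The allocation ratio is not stated; equal allocation is assumed, giving 20 per group. The maximum payment is the same in both groups: 6 × 5 + 20 = 50 and 2 × 10 + 30 = 50 dollars.

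**Assumed inputs.** Visit rates and the response to outreach are not in the documents, so ranges are used.

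**Step 1: is contact unequal?** Let p be the daily chance of a visit and q = 1 − p. The mean wait for four silent days in a row is (1 − q⁴)/(p q⁴).
- 3 visits a week (p = 3/7): q⁴ = 0.1066, so the wait is 0.8934/0.0457 = 19.55 days.
- 2 visits a week (p = 2/7): q⁴ = 0.2603, so the wait is 0.7397/0.0744 = 9.95 days.

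The ratio is 19.55/9.95 = 1.97. Simulation over 42 days gives 2.04 and 4.04 alerts per woman, again about double. The mechanism is real, but only if the incentives change sign-on: at equal rates the alerts are equal.

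**Step 2: how far does the difference move?** Here each contact adds 0.6 to the next day's visit probability in both groups, and every further four silent days counts as a new alert. Alerts are shown without any outreach effect.

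| Visits/week, usage-paid vs survey-paid | Alerts per woman | Difference in visits/week, without → with outreach effect | Difference in weeks with ≥3 visits, without → with |
|---|---|---|---|
| 3 vs 3 | 2.04 vs 2.04 | 0 → 0 | 0 → 0 |
| 3 vs 2.5 | 2.04 vs 2.95 | 0.50 → 0.41 (18% less) | 0.95 → 0.82 (14% less) |
| 3 vs 2 | 2.04 vs 4.04 | 1.00 → 0.82 (18% less) | 1.94 → 1.78 (8% less) |
| 3 vs 1 | 2.04 vs 6.74 | 2.00 → 1.59 (20.5% less) | 3.45 → 3.48 (flat) |
| 4 vs 2 | 0.79 vs 4.03 | 2.00 → 1.69 (15.5% less) | 3.32 → 2.95 (11% less) |

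**Step 3: other assumptions.** Take 3.5 vs 2.0 or 3.0 vs 1.5 visit-days a week, with a contact prompting a next-day visit with probability 0.3 to 0.8.
- Equal response, repeat contact every four silent days: the visit-day difference falls from 1.50 to between 1.40 and 1.15, a loss of about 7 to 24% before rounding. When women vary in their own visit rate, the difference in weeks with at least three visit-days is diluted by about 0 to 6%.
- One contact per lapse, which the text allows equally well, with women varying: the contact ratio is about 1.35 to 2.1, visit-day dilution about 1 to 15%, and the weeks measure between no change and about 6% dilution.
- Only the usage-paid group responds (0.8 vs 0): the visit-day difference grows from 1.50 to between 1.59 and 1.79. The direction is therefore not fixed.

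**Step 4: compare with precision.** At 20 per group, with variation between women, the 95% half-width for the visit-day difference is 0.64 to 1.00 per week, against a shift of 0.12 to 0.35 under equal response. Power moves from 0.77–0.94 without outreach to 0.74–0.93 with it. For a difference in proportions near 0.5, the half-width is 1.96 × √(2 × 0.25/20) = 0.31.

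**Step 5: what would be lost without a log?** The site supplies visit days for each participant, so the date on which each alert fell due can be rebuilt by woman, group and week. Only the actual contact date, its mode and whether she was reached would be missing.

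**The case for a change.** The best case for acting is that the contact record must be kept as the study runs, costs little, and describes something a descriptive pilot ought to describe. Staff outreach is itself a cost and a design choice for the larger trial. One could add time to first 4-day lapse as an outcome, since it is complete before any lapse contact reaches that woman. The silence in the Analysis section is real, and the mechanism stands up under independent calculation.

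What stands is a reporting suggestion. A log would describe the imbalance but would not separate payment from contact, because the contacts are themselves caused by non-use after randomisation.

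The first-lapse outcome is a doubtful gain. Three visits on consecutive days meet the weekly target yet leave 7 − 3 = 4 silent days, so a fully compliant woman can count as lapsed. At an assumed 3 visits a week about 91% have at least one alert by day 42, so a contrast at that point is near its ceiling. Its power at 20 per group is also lower: 0.58 to 0.74, against 0.74 to 0.93 for visit-days.

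Wanting the effect of payment with no outreach is a different question from the one Aim 3 poses. Nothing in the plan asks for it. That the Analysis section sets out no by-group comparison for Aim 3 is a separate matter and does not turn on outreach.

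**Conclusion.** The concern does not call for a change. Outreach follows one rule for all women, so randomisation protects the comparison of the two incentives as delivered, and following the plan gives a sound answer to Aim 3. If both groups respond equally to outreach, the likely effect is a somewhat smaller difference: about 1 to 24% for visit-days, and near zero to about 14% for weeks with at least three visits. Both are small beside the sampling error at about 20 per group. If the groups respond differently, the visit-day difference may instead be unchanged or grow.

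All of this rests on assumed visit rates and responses, independent days and equal allocation. Ratios of contacts near 2 or above mostly presuppose a large incentive effect; at 3 vs 2.5 visits a week the ratio is only about 1.2 to 1.4.

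An analyst would sensibly describe the result as the incentive effect in the presence of outreach. Keeping a dated contact log and tabulating contacts per woman by group would help the planners of the larger trial, but the validity of this one does not depend on it.

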This study will only enroll non-Caucasian women. African-American women face twice the risk of perinatal death compared to white women. They have similar rates of depression and post-traumatic stress disorder after a loss but are far less likely to seek mental health care. In previous research, bereaved African-American mothers expressed strong interest in on-line support but most were unaware this existed at the time their baby died. For this pilot MDHHS will send mailings to 200 recently bereaved non-Caucasian mothers. Assuming a 20% response rate, this will enroll 40 women in the study. We are requesting approval for up to 75 mothers in case more women respond than we anticipate. (We had a 22% participation rate among this group in the Michigan Mothers Study). MDHHS will send the initial condolence card no earlier than 3-weeks or later than 8-months post-loss.

Inclusion criteria: Michigan residence and delivery; age 18 or older at delivery; non-Caucasian race and/or Hispanic ethnicity; read/speak English; gave birth to a stillborn baby or had an infant death in the first 28 days of life; did not give the baby up for adoption pre-loss; and internet access.

Mailings: MDHHS will send the initial condolence card followed by up to three survey invitations and a reminder post-card per Dillman protocol. The mailings will include a cover letter from MDHHS. The three invitations will also include a pre-stamped card which subjects may send back to the study team if they do not want to participate. The card contains only a random study ID. The study team will report this ID to MDHHS who will then remove the subject from their subsequent mailing lists.

Consent: Study invitations will describe the study and provide mothers with an online link to learn more about the study, email (or call) the study team with questions, answer eligibility screening questions, and to complete the full written consent on-line. This is a single-arm study to test recruitment and engagement.

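### Aim 3 is a randomised comparison of two incentive schemes, but the Analysis section names no engagement measure and no summary by incentive group

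*Combined protocol and SAP*

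**What the plan says.** Proposed Study and Aims gives Aim 3 as "To test whether incentives based on group usage (compared with incentives based on survey completion) lead to increased engagement with the online group". The Incentives section repeats that comparing incentives is a study aim and supplies the mechanism: "We will randomize participants either to a group which" is paid for visiting the group, or to one paid for surveys. Both groups are also paid for the closing interview, at different rates.

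Tracking Usage lists what BabyCenter will supply for each participant: days and numbers of visits, page views, URLs, posts, comments and hugs. None is designated as the Aim 3 measure. Every woman is asked to "Sign on to the BabyCenter community group for people with pregnancy or infant loss at least 3x weekly for 6 weeks" (Participation, item a), and three visits in a week is also the payment trigger in the usage-incentive group. Posting and commenting are optional.

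The Consent paragraph says "This is a single-arm study to test recruitment and engagement", and the Analysis section says "This single-arm feasibility study will primarily be descriptive and provide summary-type information". The rest of the Analysis section covers mental health and grief outcomes (acknowledged as unpowered), the general purpose of showing that women can be recruited, retained and engaged, willingness to complete the measures, and qualitative coding. It does not mention the incentive groups.

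**The concern.** A stated aim with its own randomisation has no corresponding line in the analysis. Two things are at stake.

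The first is Aim 3 itself. A summary of the whole cohort cannot say whether one scheme produced more engagement than the other. With several usage measures available and none chosen, a comparison made later could also rest on whichever measure looked best. Payment follows visits, so visits could rise without posts or comments rising, and the measures need not agree.

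The second is the feasibility figures. The Analysis section counts willingness to complete the measures among what the pilot should show, and Proposed Study and Aims says "Once this pilot is completed, we will have adequate data and knowledge to develop a much larger randomized control study". The incentives act directly on visits, surveys and the interview. A pooled rate for any of these averages over two payment schemes and may describe neither.

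**Working it through.** **1. The plan's own figures.** Subjects and Sample Size: 200 mailings × 0.20 response = 40 women, as stated, with approval sought for up to 75. Incentives: usage group 6 × $5 + $20 = $50; survey group 2 × $10 + $30 = $50. Both match the stated maximum. There is no numerical error.

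**2. The payment contrast.** The totals are equal, but the components are not:

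| Activity | Usage-incentive group | Survey-incentive group |
|---|---|---|
| Group visits | up to 6 × $5 = $30 | $0 |
| Two surveys | $0 | 2 × $10 = $20 |
| Interview | $20 | $30 |

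Each activity used to judge engagement or data completeness is therefore paid differently in the two groups. An overall rate is the average of the two group rates, weighted by group size. The documents give no engagement or completion rates, so the distance between the overall rate and each group's rate cannot be calculated.

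**3. Following Aim 3 through the document.**
- Comparison: stated in Aim 3.
- Allocation: randomised, in Incentives.
- Data: per participant, in Tracking Usage.
- Outcome measure: not named. The three-visit threshold appears only as a request to participants and as a payment rule.
- Summary by group: not stated in Analysis.

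The gap is in selection and analysis, not in design or data collection.

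**4. What a by-group estimate would deliver.** Assume 1:1 allocation (the ratio is not stated) and all randomised women analysed. The 95% half-width for a difference in means, in SD units, is t(0.975, n1 + n2 − 2) × √(1/n1 + 1/n2).
- 40 women, 20 v 20: 2.024 × √(1/20 + 1/20) = 2.024 × 0.316 = 0.64 SD.
- 75 women, 37 v 38: 1.993 × √(1/37 + 1/38) = 1.993 × 0.231 = 0.46 SD.

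If allocation were about 2:1, the half-widths would be 0.68 SD (27 v 13) and 0.49 SD (50 v 25), so the message does not depend on the ratio.

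For a count of 0 to 6 weeks meeting the threshold, the documents give no SD. The largest it could be is about (6 − 0)/2 = 3 weeks, with half the women at 0 and half at 6. That caps the half-width at about 0.64 × 3 = 1.9 weeks with 40 women and 0.46 × 3 = 1.4 weeks with 75. A smaller SD shrinks these in proportion.

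**The case against.** The best defence is that the plan already implies the comparison. Aim 3 states it and Incentives randomises for it, and the aim cannot be met without by-group figures. Single-arm can fairly be read as one support condition, since all women receive the same group, texts and calls. Primarily descriptive does not exclude a descriptive table by group. This stands, and it limits the point. A reader might infer that nothing in the plan commits to by-group results, or that Aim 3 has been dropped. The documents do not support that: the commitment is in the aim and the randomisation, and what is missing is its counterpart in the Analysis section.

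A second defence is that the measure is nearly obvious, because three visits a week is both what every woman is asked to do and what the usage group is paid for, while posting is optional. That narrows the choice but does not settle it. The threshold is never named as the Aim 3 outcome, and because it triggers payment in one group it should not stand alone.

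A third is that this is an unpowered pilot. That excuses the absence of a formal test or a power calculation, and neither is asked for here. The sentence on power concerns the mental health and grief outcomes. It does not remove the need to say how the randomised groups will be summarised.

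**Conclusion.** The point holds as a mismatch between a randomised aim and an analysis written for a single arm. It should be fixed, but it does not undermine the study: allocation and data collection already allow the comparison. The harm is conditional. If the Analysis section is followed literally, Aim 3 may go unanswered, and pooled figures for engagement, survey completion and interview completion would blend differently paid women.

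A reader might go further and conclude that the pooled figures will mislead by a known amount. The documents give no rates from which to calculate one, so only the payment contrast ($30 v $0, $0 v $20, $20 v $30) can be stated. The half-widths of about 0.64 SD at 40 women and 0.46 SD at 75 rest on 1:1 allocation and on every randomised woman contributing usage data. They show that the comparison can be estimated but is imprecise, and so exploratory.

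**What to change.** In Consent and Analysis, describe the study as one support intervention with two randomised incentive groups. Then add an Aim 3 paragraph to Analysis that does the following:

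- Names one main engagement measure in advance. One option is the number of the 6 weeks with at least three logged visits, analysed in all randomised women by assigned group. Another measure would serve if named before the data are seen.
- Shows total visits, page views and posts or comments beside it, because the three-visit threshold is also the payment trigger in the usage group.
- Reports the between-group difference with a 95% confidence interval, labelled exploratory.
- Shows retention, survey completion and interview completion by incentive group as well as overall.

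The cost is a few sentences and one extra table. BabyCenter already supplies usage per participant, and no additional women or procedures are needed. The downside is an imprecise estimate that must not be read as a confirmatory result.
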